16.6 Handling Missing Data

In the statistical analysis of the primary effectiveness endpoint of the study, only subjects with evaluable endpoint will be used in the statistical analysis, i.e., a complete case analysis.

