12.3 Subject Withdrawal

Subjects may discontinue from the study at any time. A subject may be discontinued from the study for the following medical or administrative reasons:

- **Subject Withdrawal of Consent** - Subjects will be free to discontinue from the study at any time and for any reason but must notify the study site of their exit from the study.
- **Adverse Event** – If during the procedures the subject suffers an AE that, in the judgment of the PI, Sponsor or medical monitor, presents an unacceptable consequence or risk to the subject, the subject will be discontinued from further participation in the study.
- **Lost to Follow Up** – Subjects discontinue from the study without notifying the study site.
- **Serious Protocol Violation** – If, during enrollment in the study, the subject fails to follow, violates or refuses to participate in any of the procedures described in the protocol then the subject will be discontinued from the study at the discretion of the Sponsor. If, at any point during the study, a subject is determined to have been erroneously enrolled into the study, the subject will be discontinued from the study due to protocol violation.
- **Other** - If the above reasons are not applicable, “Other” will be selected as the option and the appropriate reason for subject withdrawal provided.

For subjects who discontinue or are withdrawn from the study for any reason, the PI will notify the Sponsor and attempt to recover the following:

- AE occurrences since the last visit to the study site
- Concomitant medication usage since the last visit to the study site

If the subject is withdrawn at a study visit, the procedures for an early termination visit will be conducted to assess their continued well-being.

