13.5.2 Enrollment/Visit 1 (Day 1)

Subjects who meet all pre-operative inclusion/exclusion criteria will return to the study site for their surgical procedure and enrollment into the study. Upon arrival at the site and final confirmation of the pre-operative inclusion/exclusion criteria, the subject will be prepped for the surgical procedure. Final confirmation of the inclusion/exclusion criteria will be made intra-operatively, at which point subjects will be enrolled in the study if they continue to be study-eligible.

Standard post-operative care will occur for all subjects according to site procedures. The subjects will be assessed for any adverse events that have occurred following the placement of the study device and concomitant medications will be recorded. Prior to hospital discharge, the site will go over all rehabilitation procedures with the subject per the rehabilitation protocol for the study.

Enrollment/Visit 1 Tasks

- Confirm pre-operative inclusion/exclusion criteria
- Surgical Procedure
 - Confirm intra-operative inclusion/exclusion criteria
 - Use of BioWick SureLock implant
- Assess any AEs

13.5.3 3 Months/Visit 2 (Day 90 ± 14 Days)

Upon arrival at the clinic, site personnel will evaluate the subject's current pain level using the ASES. Disability and function will be assessed through evaluation of ASES scores and VR-12 Scores. The subject will be asked about any adverse health events that have occurred since implantation of the device as well as any medications they are taking.

Visit 2 Tasks

- VAS scores
- ASES scores
- VR-12 scores
- ROM measurements
- Assess AEs
- Concomitant medications

13.5.4 6 Months/Visit 3 (Day 180 ± 30 Days)

Upon arrival at the clinic, site personnel will evaluate the subject's current pain level using the ASES. Disability and function will be assessed through evaluation of ASES scores, and VR-12 Scores. The subject will be asked about any adverse health events that have occurred since the last study visit as well as any medications they are taking.

Visit 3 Tasks

- VAS scores
- ASES scores
- VR-12 scores
- ROM measurements
- Assess AEs
- Concomitant medications

13.5.5 12 Months/Visit 4 (Day 365 ± 30 Days)

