Upon arrival at the clinic, site personnel will evaluate the subject's current pain level using the ASES. Disability and function will be assessed through evaluation of ASES scores, and VR-12 Scores. The subject will be asked about any adverse health events that have occurred since implantation of the device as well as any medications they are taking.

Visit 4 Tasks

- VAS scores
- ASES scores
- VR-12 scores
- ROM measurements
- Assess AEs
- Concomitant medications
- Complete Study Completion CRF

After completion of the final procedure required for this visit, the subject's participation in the study is complete, and the site should fill out the Study Completion Case Report Form (CRF).

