16.3 Analysis Populations

The following analysis populations will be defined for the study:

ITT Population – The ITT population will consist of all subjects who have signed informed consent, been enrolled in the study, and have had a successful placement of the BioWick SureLock implant.

Safety Population – The safety population will consist of all subjects who have signed informed consent, been rolled in the study and have had a procedure during which placement of the BioWick SureLock implant was attempted, whether or not placement was successful.

The primary analysis population for all primary and secondary endpoints will be the ITT population. The primary analysis population for safety will be the safety population.

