16.5 Statistical and Analytical Plans

16.5.1 Primary Endpoint Analyses

Implant survivorship for each subject will be determined by whether the subject undergoes a revision or reoperation of the study device. Survivorship will be assessed using a Kaplan-

Meier analysis. Data will be considered right-censored for all patients that do not have a device failure. For patients lost-to-follow-up, their last available clinical visit will be used as the censored date. For patients that die during the study, their death date will be used as the censored date. The survivorship point estimate and 95% confidence interval about the point estimate will be calculated for the one-year primary endpoint.

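### Sections 16.5.1 (Kaplan-Meier with censoring) and 16.6 (complete case, with the evaluable endpoint undefined) give different rules for the primary endpoint, and nothing says which governs

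*Combined protocol and SAP*

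**What the plan says.** Section 16.5.1 (Primary Endpoint Analyses) names Kaplan-Meier as the method and then sets the censoring rule: "Data will be considered right-censored for all patients that do not have a device failure". It adds dates for two groups. The first is "For patients lost-to-follow-up, their last available clinical visit will be used as the censored date"; deaths are censored at the date of death. A point estimate and 95% confidence interval are to be given at one year.

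Section 16.3 (Analysis Populations) states: "The primary analysis population for all primary and secondary endpoints will be the ITT population". That population is defined by consent, enrolment and successful placement, with no condition on follow-up.

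Section 16.6 (Handling Missing Data) says of the primary effectiveness endpoint that "only subjects with evaluable endpoint will be used in the statistical analysis, i.e., a complete case analysis". The term *evaluable* appears nowhere else and is not defined.

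Section 16.2 sizes the study on a binomial proportion: 59 subjects at 85% survivorship, raised to 71 for 15% loss to follow-up. The statistical text in the synopsis names neither Kaplan-Meier nor complete case.

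**The concern.** A subject lost at month 5 cannot both stay in the risk set until the last visit (16.5.1) and be left out because the endpoint is incomplete (16.6). The same holds for a subject who dies. The study has one primary number, and both its value and its denominator depend on which section the analyst follows.

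The study is open-label with a single arm (11.1.2), and 16.7 allows an interim analysis at any time, so the choice could be made after outcomes are known. Following 16.6 literally also removes subjects from the ITT population that 16.3 makes primary.

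**Working it through.** **1. The plan's own figures (16.2).** Inputs: p = 0.85, n = 59, stated half-width 10.7%, loss 15%, N = 71.
- Wald half-width: 1.96 × √(0.85 × 0.15 / 59) = 0.091, or 9.1 points. The Clopper-Pearson value is 9.8. The stated 10.7 is not reproduced; by Wald it corresponds to about n = 43.
- Inflation for loss: 59 / (1 − 0.15) = 69.4, so 70 against the stated 71.

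Neither difference drives this point. What matters here is that the half-width is about 9 points and that the sizing is for a simple proportion among subjects remaining after loss.

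**2. Who is treated differently.**

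| Subject | 16.5.1 | 16.6, read literally |
|---|---|---|
| Recorded device failure | event | counted as failure |
| Failure-free to 12 months | censored at end of follow-up | counted as survivor |
| Lost before 12 months | kept, censored at last visit | dropped |
| Died before 12 months without failure | kept, censored at death | dropped |

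**3. Direction.** Kaplan-Meier is S = Π(1 − dᵢ/nᵢ) over failure times. Suppose every recorded failure is evaluable and completers are followed to at least Day 365. The complete-case proportion is then the same product, with the same dᵢ but with the later-censored subjects removed from each nᵢ. No factor can be larger, so complete case is never above Kaplan-Meier. The two are equal if all losses precede the first failure.

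**4. Size.** Assumptions: N = 71, true survivorship 85%, 15% non-informative loss. Event timing is not in the documents, so a range is shown. The expected complete-case value is P(failure-free and retained) / [P(failure-free and retained) + P(failure observed)], where P(failure-free and retained) = 0.85 × 0.85 = 0.7225.
- All losses at day 0: P(failure observed) = 0.15 × 0.85 = 0.1275, and 0.7225 / 0.85 = 85.0%. Gap 0.
- Failures and losses spread evenly, exact dates: 0.15 × (1 − 0.15/2) = 0.13875, and 0.7225 / 0.86125 = 83.9%.
- Failures in months 0–3, losses in months 3–12: all failures observed, and 0.7225 / 0.8725 = 82.8%.

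Simulation (6,000 trials per scenario):

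| Timing | Kaplan-Meier | Complete case | Mean gap (points) | 97.5th percentile of single-trial gap |
|---|---|---|---|---|
| Even, lost dated to last visit | 84.5% | 83.8% | 0.7 | – |
| Even, exact dates | 84.9% | 83.8% | 1.1 | 2.4 |
| Early failures, later losses | 85.0% | 82.8% | 2.2 | 4.3 (exact dates); 4.4 (last-visit dating) |

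Complete case was never the higher of the two in any of these runs. With early failures the mean gap is 2.7 points at 80% survivorship and 0.8 at 95%. With even timing and exact dates the mean half-widths are 8.5 points (Kaplan-Meier) and 9.1 (complete case).

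**5. One data set.** Take 9 failures, 11 lost and 51 completers (9 + 11 + 51 = 71). Complete case is 51/60 = 85.0%. Kaplan-Meier is 85.0% if all losses come before the first failure, and 62/71 = 87.3% if all failures come before the first loss.

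**6. Informative loss (even timing, exact dates, 15% loss overall).**
- Would-be failures lost twice as often: the loss rate in the others is 0.15 / (0.85 + 2 × 0.15) = 0.1304. Complete case is 0.7391 / 0.8696 = 85.0%; Kaplan-Meier averages 86.0%.
- Three times as often: complete case is 0.7519 / 0.8760 = 85.8%; Kaplan-Meier averages 86.7%.

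Kaplan-Meier is then too high. Complete case is at or slightly above the true 85%, and closer to it.

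**The case against.** The best defence is that 16.5.1 is the specific rule and 16.6 a generic sentence. Under Kaplan-Meier every implanted subject supplies either a failure or a censored time, so 16.6 may mean only that no outcome is imputed. That reading keeps all of 16.5.1 operative, whereas the literal reading makes its rules for lost subjects and deaths pointless. This has force: the two sections are not beyond reconciling. But the restriction in 16.6 would then exclude almost nobody, the sentence is worded as an exclusion, and 16.2 plans for a proportion among those remaining after loss, which favours complete case. The plan does not settle the question.

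It is also fair that complete case may do better under informative loss, and that the gap is small beside the confidence interval. Both limit the severity; neither removes the need for one rule.

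Three stronger inferences are tempting, and the documents do not support them:
- *Complete case could come out higher because Visit 4 may fall as early as Day 335.* This requires reading Kaplan-Meier at Day 365 while counting subjects last seen at Day 335–364 as complete, which mixes two definitions of 12 months. It is not a consequence of 16.5.1 against 16.6.
- *Evaluable could mean attending Visit 4, so that revised subjects drop out and survivorship is inflated.* The synopsis and 16.5.1 define the outcome by whether a revision or reoperation occurs, so a recorded revision is an observed endpoint whether or not Visit 4 was attended.
- *The missing censoring date for withdrawn subjects decides which estimate is higher.* Section 16.5.1 already censors all non-failures; only the date is unstated, and no calculation shows that it changes the order.

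**Conclusion.** The concern holds as a real but modest ambiguity in the primary analysis. Read literally, 16.5.1 and 16.6 conflict for lost subjects and deaths, *evaluable* is undefined, and nothing says which section governs.

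Under the assumptions of step 4, with failures always evaluable and completers followed to at least Day 365, following 16.6 lowers the estimate by 0 to 2.2 points on average. The 97.5th percentile of the single-trial gap is about 4.4 points in the least favourable timing examined. These sizes rest on assumed event timing. Under informative loss both estimates can be biased upward, and complete case may be the nearer one.

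No hypothesis test or performance goal depends on the figure, and the half-width is about 9 points by recalculation (10.7 as stated). It should be fixed because it concerns the only primary number and costs almost nothing, not because it threatens the study's conclusion.

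Two details in 16.5.1 are also missing but are separate from the conflict. Section 12.3 lists consent withdrawal, adverse event, protocol violation and other reasons apart from loss to follow-up, yet only loss and death have censoring dates. And since at Visit 4 (Day 365 ± 30) "the subject's participation in the study is complete", some completers end follow-up before Day 365, and the plan does not say at what time the one-year estimate is read.

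**What to change.** - **16.6:** replace the complete-case sentence with: *All ITT subjects enter the Kaplan-Meier analysis of 16.5.1; subjects without device failure are censored and no outcome is imputed.*
- **Sensitivity analysis:** report any complete-case proportion only under that label, with *evaluable* defined so that every recorded revision, reoperation or removal counts as evaluable. It is worth having if loss may be related to failure.
- **16.2:** note that the binomial calculation is a planning approximation to the Kaplan-Meier analysis.
- **16.5.1 (secondary clarifications):** state the censoring date for withdrawn subjects, for example the last clinical visit as for lost subjects. State also whether the one-year estimate is read at Day 365 or over the Visit 4 window (Day 335–395).

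The cost is wording only: one sentence replaced and a few short statements added. Sample size does not change, and no new data are needed.

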16.7 Interim Analysis

Interim analysis can be performed at any point during the duration of the study.

17. ADVERSE EVENTS AND SERIOUS ADVERSE EVENTS

Equipment, supplies, and properly skilled personnel must be available to treat any unexpected reaction.

17.1 Safety

Although major AEs are not anticipated, the investigator must proceed with utmost caution.

The AEs reported will be evaluated as to incidence, relationship to the time the device was used, how long the device had been in use, severity, and relationship to the medical device.

The section on AEs will be tabulated by severity and by Investigator's assessment of the event's causative relation to treatment. AE counts by severity level (mild, moderate, and severe) will be tabulated.

17.2 Definitions

The term "adverse event," as used by the Sponsor, is synonymous with the term "adverse experience," which is used by the FDA.

An *adverse event* for a device is defined as "untoward medical occurrence". An adverse event is an untoward occurrence that is temporally associated with, but not necessarily related to or caused by, the use of the device. If the untoward medical occurrence does not involve a subject, only occurrences related to the investigational device are included in the definition and handled by the Sponsor's adverse event system.

A **serious adverse event** is defined as any untoward medical occurrence that meets the following criteria:

1. Results in death (i.e., the AE actually causes or leads to death)
2. Is life-threatening (i.e., an AE that, in the opinion of the Investigator, places the subject at immediate risk of death)
3. Requires in-patient hospitalization or prolongs an existing hospitalization (i.e., the AE requires hospitalization lasting at least 24 hours or prolonged hospitalization beyond the expected amount of time; hospitalizations for scheduled medical or surgical procedures to conduct scheduled treatments or routine examinations of SAEs do not meet these criteria)
4. Results in persistent or significant disability or incapacity (i.e., the AE causes substantial disruption in the ability of the subject to carry out normal activities)
5. Is a congenital anomaly or birth defect in the infant/ newborn of a mother that has been exposed to the research compound
6. Is considered by the Investigator to be significant medical event based on medical criteria (e.g., puts the subject at risk or may require medical or surgical intervention to prevent one of the aforementioned results)

The seriousness must be evaluated independently from the severity when documenting the AEs on the CRF.

Additionally, important medical events that may not result in death, be life threatening, or require hospitalization may be considered SAEs when, based on appropriate medical judgment, they may jeopardize the subject and may require medical or surgical intervention to prevent one of the outcomes listed above.

A **life threatening adverse event** is any AE that places the subject at immediate risk of death from the event as it occurred. A life-threatening event does not include an event that might have caused death had it occurred in a more severe form but that did not create an immediate risk of death as it actually occurred.

Hospitalization is to be considered only as an overnight admission. Hospitalization or prolongation of a hospitalization is a criterion for considering an AE to be serious. In the absence of an AE, the participating investigator should not report hospitalization or prolongation of hospitalization on a form.

In addition, a hospitalization planned before the start of the study for a preexisting condition that has not worsened does not constitute an SAE (e.g. elective hospitalization after the procedure was performed and before study completion).

Disability is defined as a substantial disruption in subject's ability to conduct normal life functions.

17.3 Reporting of Serious Adverse Events

This section will address the reporting of the serious adverse event to the Sponsor and/or their representatives.

In the event that any SAEs occur during this study, the Investigator will notify the Sponsor or the Sponsor's safety representative via fax or phone immediately after becoming aware of the incident.

The Investigator will fax the SAE Report Form, and other documentation regarding the SAE to the Sponsor or the Sponsor's safety representative. The Investigator will promptly provide follow-up information requested by the Sponsor or the Sponsor's safety representative.

17.4 Collecting, Recording and Reporting Adverse Events

Adverse events will be recorded from the time a subject has signed the ICF until the subject terminates from the study. The Investigator is responsible for ensuring that all AEs are observed and reported during the study on the corresponding AE page of the CRF.

The Investigator will collect AE data at all stages of subject evaluation during the study. AEs will be recorded stating the duration (i.e., onset and resolved dates) of the event, the intensity, the relationship to the device, the relationship to the surgical procedure, action taken, the outcome, the seriousness, regulatory criterion, if any, and the presumed association with the study.

Note: The AE must be recorded on the AE page of the CRF. Each AE should be marked appropriately on the AE page as to whether it is serious. An SAE must be reported to the Sponsor or the designated safety personnel as soon as possible after the Investigator has become aware of its occurrence.

The causal relation between an AE and the study device will be determined by the investigator on the basis of his or her clinical judgment and the following definitions:

- **Definitely related:** Event can be fully explained by administration of the study device.
- **Possibly related:** Event may be explained by administration of the study device or by the subject's clinical state or other agents/therapies.
- **Not related:** Event can be fully explained by the subject's clinical state or other agents/therapies.

When assessing the relationship between the study device and an AE, the following should be considered:

1. Temporal relationship between the administration of the study device and the AE;
2. Biological plausibility of relationship;
3. Subject's underlying clinical state;

4. When applicable, whether the AE abates on discontinuation of the use of the study device.

SAEs that are not study related may nevertheless be considered by the participating investigator or the medical monitor (or designee) to be related to the conduct of the clinical study, i.e., to a subject's participation in the study. For example, a protocol-related SAE may be an event that is related to another non-test procedure required by the protocol.

The following definitions should be used when determining the severity of an AE.

- **Mild:** The AE is noticeable to the subject but does not interfere with activity.
- **Moderate:** The AE interferes with routine activity but responds to symptomatic therapy or rest.
- **Severe:** The AE significantly limits the subject's ability to perform activities despite symptomatic therapy.

18. STUDY SUSPENSION, TERMINATION, AND COMPLETION

The Sponsor may suspend or terminate the study or part of the study at any time for any reason. If the investigator suspends or terminates the study, the investigator will promptly inform the Sponsor and the IRB and provide them with a detailed written explanation. Upon study completion, the investigator will provide the Sponsor, IRB, and regulatory agency with final reports and summaries as required by regulations. The investigator must submit a written report to the Sponsor and the IRB within three months after the completion or termination of the study. Study termination and follow-up will be performed in compliance with the Sponsor's or designee's standard procedures.

18.1.1 Termination by the Sponsor

The Sponsor may terminate the study, or the study site, at any time for any of the following reasons:

1. Failure to enroll subjects
2. Protocol violations
3. Inaccurate or incomplete data
4. Unsafe or unethical practices
5. Questionable safety of the study device
6. Suspected lack of appropriateness of the study device
7. Administrative decision

